2.1 Primary Objective

To demonstrate the non-inferiority^a, in terms of geometric mean of titer ratios (GMTRs), of a CYD dengue vaccine booster compared to the third CYD dengue vaccine injection in subjects from CYD 28 trial (subjects from Group 1 only).

2.2 Secondary Objectives

Immunogenicity

- 1) If the primary objective of non-inferiority is achieved: To demonstrate the superiority, in terms of GMTRs, of a CYD dengue vaccine booster compared to the third CYD dengue vaccine injection in subjects from CYD28 trial (subjects from Group 1 only).
- 2) To describe the immune responses elicited by the CYD dengue vaccine booster or placebo injection in subjects who received three doses of the CYD dengue vaccine in the CYD28 trial in all subjects.
- 3) To describe the neutralizing antibody (Ab) levels of each dengue serotype PD3 (CYD28 subjects) and immediately prior to booster or placebo injection for all study subjects.
- 4) To describe the neutralizing Ab persistence 6 months, 1 year and 2 years post booster or placebo injection for all study subjects.

Safety

To evaluate the safety of booster vaccination with CYD dengue vaccine in all subjects.

2.3 Additional Objectives

Only for the additional immunological tests (AIT) subset

- 1) To describe dengue neutralizing Ab levels (exploration of the Ab response's kinetics), Ab specificity and affinity maturation post-booster or placebo injection
- 2) To describe cell mediated immunity (CMI) responses post-booster or placebo injection.

^a If the planned sample size is not achieved, the analysis may be descriptive.

In all subjects

- 3) To assess post-booster neutralizing Ab levels against each dengue virus serotype while controlling for baseline neutralizing Ab levels against each dengue virus serotype

3 Description of the Overall Trial Design and Plan

3.1 Trial Design

This is a multi-center, observer-blind, randomized, placebo-controlled, Phase II trial of the CYD dengue vaccine booster in 260 healthy subjects aged 9 to 45 years on the day of the first injection of study vaccine, and who received 3 doses of the CYD dengue vaccine in the CYD28 trial in Singapore.

There will be 1 vaccination at Day (D) 0 and 2 groups of subjects:

- **Group 1:** 195 subjects will receive CYD dengue vaccine booster
- **Group 2:** 65 subjects will receive placebo

A total of 60 subjects (45 subjects in Group 1 and 15 subjects in Group 2) will also be included in a specific subset (AIT subset).

The duration of each subject's participation in the trial will be approximately 24 months.

3.2 Trial Plan

Eligible subjects will be identified by the Sponsor. Each investigator will be provided with a list of potential subjects to recruit. Once enrolled, each subject (and subjects' parent(s) / legally acceptable representative(s) for subjects aged < 21 years) will sign and date consent forms (ICF). All included subjects will attend 5 study visits and will receive 9 phone calls. Subjects from the AIT subset will attend 2 additional study visits:

- Study visits at Day (D) 0, D28, Month (M) 6, M12, M24 after vaccination
- Additional study visits for subjects in AIT subset: D7 and D14
- Phone calls at M2, M4, M8, M10, M14, M16, M18, M20, and M22 after vaccination

Vaccination

All subjects will receive either CYD dengue vaccine booster or placebo on D0.

Blood sampling

- For all subjects

Immunogenicity will be assessed at baseline (D0), as well as 28 days, 6 months, 1 year and 2 years post-vaccination.

- For the AIT subset

A subset of 60 subjects (45 subjects in Group 1 and 15 subjects in Group 2) will provide additional blood samples at baseline and at 7, 14, 28 days, and 1 year post-injection. Depending on the time points, these blood samples will be used for measurement of CMI, Ab specificity and affinity maturation, and neutralizing Ab (exploration of the Ab response's kinetics).

Collection of safety data

Clinical site personnel will record immediate adverse events (AEs) that occur within the 30 minutes after injection. Subjects or subjects' parent(s) / legally acceptable representative(s) will record in the diary card (DC) information about solicited injection site reactions from D0 to D7 post-injection, about solicited systemic reactions from D0 to D14 post-injection and unsolicited AEs from D0 to D28 post-injection. Information on non-serious adverse events of special interests (AESIs) will be collected within 7 days post-injection. Information on serious adverse events (SAEs) (including serious AESIs) will be collected throughout the trial. Subjects or subjects' parent(s) / legally acceptable representative(s) are to contact the Investigator in case of hospitalization for suspected dengue disease.

Subjects or subjects' parent(s) / legally acceptable representative(s) will record safety information in memory aids (MAs) when DCs are not being used. Clinical site personnel will record information about SAEs and serious AESIs written in the MAs.

See [Table 3.1](#) for details of study procedures.

Table 3.1: Study procedures

Phase II Trial, 5 or 7 Visits, 1 Vaccination, 5 or 7 Blood Samples, 9 Phone Calls, 24-Month Duration per Subject

Visit Number (V)	V01	V02*	V03*	V04	PC1	PC2	V05	PC3	PC4	V06	PC5	PC6	PC7	PC8	PC9	V07
Trial Timelines (Days/Months)	D0	V01 + 7d	V01 + 14d	V01 + 28d	V01 + 2M	V01 + 4M	V01 + 6M	V01 + 8M	V01 + 10M	V01 + 12M	V01 + 14M	V01 + 16M	V01 + 18M	V01 + 20M	V01 + 22M	V01 + 24M
Time Windows (Days)		+2	+7	+7	+8d	+8d	+20d	+8d	+8d	±30	+8d	+8d	+8d	+8d	+8d	±30
Informed Consent	√															
Inclusion/Exclusion Criteria	√															
Demography/Body Stature	√															
Significant Medical History	√															
History of dengue infection	√															
Physical Examination and Temperature†	√	√	√	√			√			√						√
Urine Pregnancy Test‡	√															
Concomitant Therapy	√	√	√	√												
IVRS/IWRS Call	√*															
Blood Sampling: Neutralizing Ab PRNT (all subjects)	BL1§			BL4			BL5			BL6						BL7
Injection	Inj. 1															
30-Min. Observation Period	√															
Injection Site Reactions & Systemic Events Assessment**	√	√	√	√												
Diary Card (DC) Provided Checked & Collected	DC	DC	DC	DC DC												
Memory Aid (MA) Provided Checked				MA	MA	MA	MA	MA	MA	MA	MA	MA	MA	MA	MA	MA

Visit Number (V)	V01	V02*	V03*	V04	PC1	PC2	V05	PC3	PC4	V06	PC5	PC6	PC7	PC8	PC9	V07
Trial Timelines (Days/Months)	D0	V01 + 7d	V01 + 14d	V01 + 28d	V01 + 2M	V01 + 4M	V01 + 6M	V01 + 8M	V01 + 10M	V01 + 12M	V01 + 14M	V01 + 16M	V01 + 18M	V01 + 20M	V01 + 22M	V01 + 24M
Time Windows (Days)		+2	+7	+7	+8d	+8d	+20d	+8d	+8d	±30	+8d	+8d	+8d	+8d	+8d	±30
Phone Call††					√	√		√	√		√	√	√	√	√	
Termination Record																√
SAEs and Serious AESIs‡‡	Throughout the period															
THE FOLLOWING ADDITIONAL PROCEDURES APPLY ONLY TO THE AIT SUBSET§§																
Additional neutralizing Ab PRNT (both for adolescents and adults)		BL2	BL3													
CMI, Ab specificity and affinity maturation (for adolescents)	BL1	BL2	BL3	BL4						BL6						
CMI, neutralizing Ab (2 additional time points), Ab specificity and affinity maturation (for adults)	BL1	BL2	BL3	BL4						BL6						

* V02 and V03 are only for subjects included in the additional immunological test (AIT) subset
† Mandatory at injection visit (before injection). For other visits: physical examination and temperature measurement will be performed if necessary, based on the health status of the subject.
‡ In female subjects of childbearing potential (i.e. women and girls who have reached menarche and who had not surgical sterilization, or hysterectomy).
§ Blood samples planned during vaccination visit will be taken before vaccination
** Solicited injection site reactions will be collected for 7 days after injection. Solicited systemic reactions will be collected for 14 days after injection. Unsolicited AEs will be collected for 28 days after injection.
†† Telephone call to contact the subjects and ask them about SAEs that may have occurred
‡‡ Serious AESIs will be reported after each injection in defined time windows as follows: serious hypersensitivity/allergic reactions occurring within 7 days, serious viscerotropic disease occurring within 30 days, serious neurotropic disease occurring within 30 days; hospitalized suspected dengue disease will be reported during the entire study. Non-serious AESIs (i.e. hypersensitivity / allergic reactions) will be reported within 7 days after each injection.
§§ In the AIT subset of 60 subjects (45 subjects in Group 1 and 15 subjects in Group 2).

4 Endpoints and Assessment Methods

4.1 Primary Endpoints and Assessment Methods

4.1.1 Immunogenicity

4.1.1.1 Immunogenicity Endpoints

The primary endpoint for the evaluation of immunogenicity is:

Neutralizing Ab levels against each dengue virus serotype measured 28 days after the third CYD dengue vaccine injection and 28 days after the booster injection in Group 1 using dengue plaque reduction neutralization test (PRNT).

4.1.1.2 Immunogenicity Assessment Methods

See Section 9.1.1.2 of the protocol for assessment methods.

4.1.2 Safety

There are no primary objectives for safety.

4.1.3 Efficacy

No clinical efficacy data will be obtained in the trial.

4.2 Secondary Endpoints and Assessment Methods

4.2.1 Immunogenicity

4.2.1.1 Immunogenicity Endpoints

The secondary endpoints for the evaluation of immunogenicity are:

- 1) Neutralizing Ab levels against each of the four parental dengue virus strains of CYD dengue vaccine as determined by PRNT measured 28 days after the third CYD dengue vaccine injection received in CYD28 trial and 28 days post-booster injection (subjects from Group 1 only).
- 2) Neutralizing Ab levels against each of the four parental dengue virus strains of the CYD dengue vaccine as determined by PRNT immediately prior and 28 days post-booster or placebo injection.

- 3) Individual post-booster/pre-booster GMTRs for each of the four parental dengue virus strains of the CYD dengue vaccine as determined by PRNT immediately prior and 28 days post-booster or placebo injection.
- 4) Seroconversion rates 28 days after the injection for each of the four parental dengue virus strain of CYD dengue vaccine; percentages of subjects with either a pre-booster titer < 10 (1/dilution [dil]) and a post-booster dose titer ≥ 40 (1/dil), or a pre-booster titer ≥ 10 (1/dil) and a ≥ 4 -fold increase in post-booster dose titer as determined by PRNT immediately prior and 28 days post-injection.
- 5) Neutralizing Ab levels against each of the four parental dengue virus strains as determined by PRNT at 28 days after the third CYD dengue vaccine injection received in CYD28 trial and immediately prior to booster or placebo injection in all study subjects.
- 6) Neutralizing Ab levels against each of the four parental dengue virus strains as determined by PRNT at 6 months, 1 year and 2 years post booster or placebo injection in all study subjects.

4.2.1.2 Immunogenicity Assessment Methods

See Section 9.2.1.2 of the protocol for assessment methods.

4.2.2 Safety

4.2.2.1 Safety Endpoints

The endpoints for the evaluation of safety are:

- 1) Occurrence, nature (Medical Dictionary for Regulatory Activities [MedDRA] preferred term [PT]), duration, intensity, action taken, whether it leads to discontinuation or not, and relationship to vaccination of any AEs reported in the 30 minutes after vaccination.
- 2) Occurrence, time to onset, number of days of occurrence, intensity, whether it leads to discontinuation or not, and action taken of solicited (pre-listed in the subject's diary card [DC] and case report form [CRF]) injection site reactions (pain, erythema, and swelling) occurring up to 7 days after vaccination.
- 3) Occurrence, time to onset, number of days of occurrence, intensity, whether it leads to discontinuation or not, and action taken of solicited systemic (DC and CRF) reactions (fever, headache, malaise, myalgia, and asthenia) occurring up to 14 days after vaccination.
- 4) Occurrence, nature (MedDRA PT), time to onset, duration, intensity, whether it leads to discontinuation or not, action taken and relationship to vaccination (for systemic AEs only) of unsolicited spontaneously reported AEs up to 28 days after vaccination.
- 5) Occurrence of Serious Adverse Events (SAEs), including serious AESIs (with specific time window according to the nature of event), throughout the trial.
- 6) Occurrence, nature (MedDRA PT), time to onset, duration, intensity, action taken, and relationship to vaccination of non-serious AESIs occurring up to 7 days after vaccination.

- 7) Occurrence of hospitalized virologically-confirmed dengue cases throughout the trial (i.e., from D0 through end of the study).

4.2.2.2 Safety Assessment Methods

See Section 9.2.2.3 of the protocol for assessment methods.

4.2.3 Efficacy

No clinical efficacy data will be obtained in the trial.

4.3 Additional Endpoints and Assessment Methods

4.3.1 Immunogenicity

4.3.1.1 Immunogenicity Endpoints

Subjects from the AIT subset (i.e., the first 60 randomized subjects from 2 specific sites (30 subjects per sites; 45 subjects in Group 1, 15 subjects in Group 2).

1) Dengue PRNT

Two additional time points for neutralizing Ab levels against each of the four parental dengue virus strains as determined by PRNT at 7 and 14 days post-injection.

2) Ab specificity and affinity maturation

- a) The neutralizing Abs in the wide-type dengue parental strains (DENV) depleted, BSA-control depleted sera and whether the Ab response is homotypic for each of the four parental dengue virus strains will be assessed qualitatively immediately prior to and at 7, 14 and 28 days post-injection. For the descriptive summary of Ab response, BSA-control depleted sera are considered as undepleted and DENV depleted as depleted. Homotypic Abs for individual serotypes will be defined as a neutralizing antibody titer above 20 (1/dil) following DENV depletion.
- b) Serotype-specific affinity (KA , nM^{-1}) and Ab concentration ($\mu g/mL$) will be measured against the parental wild-type strains in the sera immediately prior to and at 28 days post-injection.

3) CMI response

The specific B and T immune response against the 4 dengue serotypes elicited by the CYD dengue vaccine booster will be assessed by the enzyme-linked immunospot (ELISPOT) or flow cytometry, using intracellular staining and phenotyping:

- a) T-cell response immediately prior to and 28 days, and 1 year after booster or placebo injection:
 - i) Cytokine secreting CD4 and CD8 T-cells count.
 - ii) T-cell subclasses (naïve, effector, central and terminally differentiated memory T cells) count.

- iii) Cytotoxic T-cell effector markers.
- b) B-cell response:
 - iv) Ex vivo B-cells (plasmablast) count (measured by ELISPOT) immediately prior to and 7 and 14 days after booster or placebo injection.
 - v) Memory B cells count (measured by ELISPOT) immediately prior to and 28 days and 1 year after booster or placebo injection for a subset of subjects.

For all subjects

- 4) Post-booster neutralizing Ab levels against each of the 4 parental dengue virus strains as determined by PRNT

The assays, along with the corresponding samples, will be managed by the specific sanofi pasteur organization (e.g., Global Clinical Immunology [GCI], Research), or with an external laboratory, as it applies.

4.3.1.2 Immunogenicity Assessment Methods

See Section 9.3.1.2 of the protocol for assessment methods.

The lower limit of detection (LLOD) for the 50% of neutralization titer by flow cytometry for Ab specificity is a titer of 20. To be able to calculate affinity, the LLOD for measuring the kinetic rates is an Ab concentration of 1 ng/mL and the the lowest dissociation constant K_D that can be reliably be measured on the instrument is 10 pM.

4.3.2 Safety

There are no additional objectives for safety.

4.3.3 Efficacy

No clinical efficacy data will be obtained in the trial.

4.4 Derived Endpoints: Calculation Methods

4.4.1 Immunogenicity

4.4.1.1 Computed Values for Analysis

For the computation of GMTs, a titer reported as < LLOQ will be converted to a value of 0.5 LLOQ.

For calculating fold-rise and titer ratio (GMTR), < LLOQ will be converted to 0.5 LLOQ for a numerator and < LLOQ will be converted to LLOQ for a denominator

There is no upper limit of quantification (ULOQ) with the PRNT method planned.

4.4.1.2 Fold-rise

The derived endpoint fold-rise is driven by computed titer values (as described in [Section 4.4.1.1](#)) and is computed as follows:

- the ratio of post-booster computed value divided by pre-booster computed

Note: If the titer value used for the above calculation is missing, then fold-rise is missing.

4.4.1.3 Seroconversion

If a pre-booster titer < 10 (1/dil) and a post-booster dose titer is ≥ 40 (1/dil) then the derived seroconversion indicator will be “Yes” for that test. Or, if a subject has a pre-booster titer ≥ 10 (1/dil) and achieves ≥ 4 -fold increase from pre to post-booster dose titer then the seroconversion indicator will be “Yes” for the test. Otherwise, seroconversion will be “No”.

4.4.1.4 Calculation rules for the “at least X serotype(s)” tables

The criteria below will be computed for each subject and visit as soon as at least one of the 4 dengue serotype result is different from missing or not-reportable (NR) (i.e. coded no result in the serology database):

- Number and percentage of subjects with antibody titer ≥ 10 (1/dil) against at least 1, 2, 3, or 4 serotypes with the parental dengue virus strains.
- Number and percentages of subjects with antibody titer \geq various titer thresholds (1/dil) against at least 1, 2, 3, or 4 serotypes with parental the dengue virus strains.

Titer(s) \geq to a threshold for at least X serotype(s) with parental dengue virus strains is computed as a Yes/No/Missing variable (note: in the case no titer is available the variable will be missing). If at least X among the 4 serotype titers meet the threshold considered then the variable is derived to “Yes”, otherwise if at least one titer is available and does not meet the threshold the variable is derived to “No”. For the percentage calculation, all the subjects with at least one titer available regardless of the serotype will be considered in the denominator.

4.4.1.5 Pre-booster dengue status

The pre-booster dengue status is defined as the presence of Abs against at least one dengue serotype in the baseline sample in the blood sample collected at V01 in the present study from all subjects.

The pre-booster dengue status is computed based on computed values of serotypes with the parental dengue virus strain at V01. If the computed value is positive (≥ 10 1/ dil) for at least one serotype then the Dengue immune indicator will be “Immune”. Else if the computed value is not positive (< 10 1/dil) and non-missing for all serotypes (i.e. all of the titers planned to be measured at baseline must be available, and valid [not coded “NR” in the serology database] then the Dengue immune indicator will be “Non-immune”. Otherwise the baseline dengue status will be classified as “Undetermined”.

In any other cases Dengue immune indicator will be missing.

4.4.2 Safety

Terms used in the clinical safety tables to describe the safety events are specified below:

- AE: Adverse event; includes immediate, solicited, and unsolicited non-serious or serious adverse events.
- AR: Adverse reaction; Adverse reaction corresponds to an unsolicited related AE
- Immediate AE/AR: Unsolicited non-serious AE ticked "immediate (within 30 minutes from the vaccination)" by the investigator in the CRF or SAE with time of onset within 30 minutes
- Solicited reaction: Event pre-listed in the CRF, and which occurred during the solicited period (period is usually 0 to 7 days for injection site reactions and 0 to 14 days for systemic reactions post-vaccination)
- Unsolicited AE: AE recorded in the eCRF unsolicited form and SAE form, excluding solicited reactions. Therefore, this term includes immediate AEs/ARs.
- Unsolicited non-serious injection site events are always recorded without relationship and analyzed as ARs.
- SAE: Unsolicited AE considered serious by the investigator.
- Hospitalized suspected dengue case: Hospitalized suspected dengue disease is defined as an acute febrile illness with diagnosis of dengue requiring hospitalization (with bed attribution).
- Hospitalized virologically-confirmed dengue case: A virologically-confirmed dengue infection is defined as a suspected dengue which has positive sample for the dengue screen RT-PCR (i.e., \geq LLOQ) and/or the non-structural protein 1 (NS1) antigen (Ag) enzyme-linked immunosorbent assay (ELISA) is positive and/or the SimplexaTM dengue reverse transcription-polymerase chain reaction (RT-PCR) is positive. Dengue NS1 Ag ELISA positive is defined as sample ratio >1 by comparing the optical density reading of the sample to the optical density of the cutoff control serum. The SimplexaTM Dengue RT-PCR positive is defined as detected results for at least one dengue serotype.

4.4.2.1 Solicited Reactions

4.4.2.1.1 Daily Intensity

All daily records for solicited reactions will be derived into daily intensity according to the following classification: None, Grade 1, Grade 2, Grade 3, or Missing.

For the derivation of daily intensities the following sequential steps will be applied:

- 1) Solicited reactions (except Fever/Pyrexia) with an investigator presence recorded as "No" and with all daily records missing then all daily intensities will be derived as None.
- 2) For non-measurable solicited reactions, daily intensities will correspond to daily records reported in the clinical database. For measurable solicited reactions the daily measurements reported in the clinical database will be converted based upon the intensity scales defined in

Section 9.2.2.3.2 of the protocol; this assumes a reaction that is too large to measure (non measurable, [NM]) is Grade 3.

Note: The maximum intensity on the ongoing period is derived from the record of the maximum intensity/measurement after the end of the solicited period following the rule described above.

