4.4.2.1.3 Presence

Presence is derived from the maximum intensity on the period considered:

- None: No presence
- Grade 1, Grade 2, or Grade 3: Presence
- Missing: Missing presence

Subjects with at least one non-missing presence for a specific endpoint will be included in the analysis. Conversely, those without a non-missing presence will not be included in the analysis of the endpoint.

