5.3.2 Safety

No replacement will be done unless state otherwise. No search for outliers will be performed. In all subject listings, partial and missing data will be clearly indicated as missing.

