5.3.2.3 Measurements

Missing measurement (for temperature or length) will not be replaced.

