5.3.2.4 Intensity

For solicited reactions, missing intensities will be handled as described in [Section 4.4.2.1.1](#). For unsolicited non-serious AEs, missing intensities will remain missing and will not be imputed.

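### The solicited-reaction rule counts an investigator 'No' with blank daily records as no reaction but drops an investigator 'Yes' with blank daily records, which can understate rates of the five graded reactions

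*SAP*

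**What the plan says.** SAP 4.4.2.1.1 derives daily intensities in two sequential steps. Step 1 exempts fever. Its rule for any other solicited reaction is: "with an investigator presence recorded as 'No' and with all daily records missing then all daily intensities will be derived as None". Step 2 covers everything else. For non-measurable reactions, "daily intensities will correspond to daily records reported in the clinical database"; for measurable ones, the recorded measurement is converted to a grade.

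SAP 4.4.2.1.2 takes the maximum of the daily intensities, and SAP 4.4.2.1.3 derives presence from that maximum. A missing maximum gives a missing presence, and "those without a non-missing presence will not be included in the analysis of the endpoint".

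The missing-data section adds no other rule. The default in SAP 5.3.2 is "No replacement will be done unless state otherwise". SAP 5.3.2.3 says "Missing measurement (for temperature or length) will not be replaced". SAP 5.3.2.4 points back to where the rule started: "For solicited reactions, missing intensities will be handled as described in" Section 4.4.2.1.1.

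**The concern.** The investigator's presence field is used in one direction only. Take two subjects with no daily records, one recorded by the investigator as having had headache and one as not. The second is analysed as a non-reactor; the first is removed from the headache analysis.

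The endpoints concerned (protocol 9.2.2.2, endpoints 2 and 3) list occurrence separately from intensity. A 'Yes' answers the question of occurrence even when the grade is unknown. The SAP's usual practice is to keep events whose details are missing: missing causality counts as related (SAP 5.3.2.2), unsolicited AEs with missing onset stay in the tables (SAP 4.4.2.2.4 and 5.3.2.5), and a reaction too large to measure is Grade 3 (SAP 4.4.2.1.1). Here the missing detail removes a recorded reaction instead.

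At stake are the percentages of subjects with solicited reactions and their confidence intervals, which form a main part of the booster's safety description.

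**Working it through.** **Plan figures.** The documents give no solicited-reaction rate and no rate of blank records, so there is no plan figure to reproduce on this point. The one safety figure in the sample-size section (SAP 5.5) does reproduce: 1 − (1 − 0.017)^176 = 0.951, against about 95% stated. It has no bearing on this rule.

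**Tracing the four blank-record cases**

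- 'No', all blank, not fever: step 1 gives None every day, so presence is No and the subject is in the denominator.
- 'Yes', all blank, not fever: step 1 does not apply and step 2 has nothing to convert. Every day is Missing, presence is Missing, and the subject is excluded.
- Fever, 'No' or 'Yes', all blank: step 1 exempts fever, so both are Missing and both are excluded. There is no asymmetry.

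The second case is never named in the SAP; its exclusion follows from reading these sections together.

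**Direction.** Let D be the subjects with daily records, R the reactors among them, Nb the 'No'/blank subjects, Yb the 'Yes'/blank subjects, and g the share of Yb whose reaction would have been Grade 1 or higher.

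- Rate under the SAP: R / (D + Nb)
- Rate with all subjects classified: (R + g·Yb) / (D + Nb + Yb)

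The SAP rate is the lower of the two exactly when Yb > 0 and g > R / (D + Nb).

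- Pain, headache, malaise, myalgia, asthenia: the scale in protocol Tables 9.1 and 9.2 starts at Grade 1 with no size threshold. A correct 'Yes' is therefore Grade 1 or higher, g is about 1, and the SAP rate is too low whenever Yb > 0 and the rate is below 100%.
- Erythema and swelling: Grade 1 starts at 25 mm, and SAP 4.4.2.1.2 notes that an investigator-recorded reaction below that size is analysed as None. Illustration with R = 20, D + Nb = 190, Yb = 5: the SAP rate is 20/190 = 10.5%. The full rate is 25/195 = 12.8% if g = 1, and 20/195 = 10.3% if g = 0. The break-even is g = 0.105.

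**Size for the graded reactions (assumed inputs).** Let r be the true rate and m the share of subjects with blank records, equal in reactors and non-reactors, with the investigator's entry correct. Then R = N·r(1 − m), D + Nb = N(1 − r·m), and the reported rate is r(1 − m) / (1 − r·m).

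| True rate r | m = 2% | m = 5% | m = 10% |
|---|---|---|---|
| 10% | 9.8% | 9.5% | 9.1% |
| 30% | 29.6% | 28.9% | 27.8% |
| 50% | 49.5% | 48.7% | 47.4% |

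The shortfall runs from 0.2 to 2.6 percentage points. In the 195 booster recipients with m = 5% and r = 30%, about 195 × 0.05 × 0.30 = 2.9 reactors would be dropped.

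**The case against.** The strongest reply is that such records should hardly exist. The rule works on records in the clinical database, not on the paper diary. Protocol 13.2 requires verbal clarification of missing diary data and its transfer to the CRF. Protocol 11.1 has information absent from the diary captured in the source document and then reported electronically, and requires explanations for missing information. Protocol 11.2 applies consistency checks and queries. An investigator who can record 'Yes, headache' should usually be able to obtain a grade. This stands as an argument about frequency. It does not supply a rule for cases that remain, and step 1 shows that all-blank records were expected.

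A second reply is that 'No' plus blank may simply be how the CRF records a non-reactor, if the daily grid is skipped after a 'No'. The documents do not show the CRF layout, so this is possible. It does not change the direction for the graded reactions: non-reactors are kept either way, and the formula then holds with m read as the share of reactors with blank records. It does mean that no value of m can be taken from the documents.

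Third, the rule is the same in both groups, safety is descriptive, and the shift is small beside sampling error. With r = 40%, m = 5% and N = 195, the reported rate is 0.38/0.98 = 38.8%, a shift of 1.2 points. The 95% half-width is about 1.96 × √(0.4 × 0.6/195) = 6.9 points. This stands and limits the weight of the point, though equal application does not make either group's percentage correct.

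**Conclusion.** The asymmetry is real for seven of the eight solicited reactions. For the five graded reactions it understates the reported percentage whenever a 'Yes'/blank subject exists, provided the investigator's 'Yes' is right. For erythema and swelling the direction is open. Fever is unaffected. The size is unknown and probably small: 0.2 to 2.6 points under the assumed 2% to 10% blank records and true rates of 10% to 50%. The primary immunogenicity test is not touched.

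Two stronger readings are tempting, and the documents support neither.

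- A reader might infer that the rule always lowers solicited-reaction rates. It does not: fever is exempt, nothing happens if no 'Yes'/blank subject exists, and the 25 mm threshold can reverse the sign for erythema and swelling.
- A reader might infer that it narrows the booster–placebo difference. The shortfall is r·m(1 − r)/(1 − r·m), which is largest at middling rates, so the difference can move either way. With m = 10%, true rates of 70% and 50% are reported as 0.63/0.93 = 67.7% and 0.45/0.95 = 47.4%, a difference of 20.4 points against a true 20.0.

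**What to change.** Amend SAP 4.4.2.1.1 to 4.4.2.1.3 as follows.

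- **Pain, headache, malaise, myalgia, asthenia:** if investigator presence is 'Yes' and all daily records are missing, derive presence = Yes with maximum intensity = Missing. Keep the subject in numerator and denominator, and show a 'Missing intensity' row.
- **Erythema and swelling:** keep the existing 'No' rule. Report the number of 'Yes'/blank subjects per group, and add a sensitivity line counting them as present. Setting 'No'/blank to Missing for the sake of symmetry would be a mistake. It discards valid non-reactors, and it could inflate the rate badly if the CRF grid is left blank after a 'No'.
- **Fever:** no change.

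The cost is one SAP rule, one extra table row, one sensitivity line and minor programming, using a field already collected. Onset and number of days will also be missing for these subjects, and SAP 4.4.2.1.4 and 4.4.2.1.5 list no missing category, so those tables need one. The downside is a few reactions shown without a grade and slightly higher reported rates. If no such subject occurs, the results do not change. The overall count can be checked at the blinded data review (SAP 5.6).
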